6. SAFETY

6.1. Analysis Specifications

6.1.1. Level of Significance

All planned analysis for this study will be conducted with a two-sided type I error rate of 5% for primary and secondary hypotheses. Adjustment for multiple comparisons across time will be performed using Bonferroni's method. Both adjusted and unadjusted results will be reported.

6.1.2. Data Handling Rules

Missing or spurious values will not be imputed for the primary or secondary hypotheses. The count of missing values will be included in the summary tables and listings.

6.2. Safety Endpoint(s)

6.2.1. Definition

The primary safety endpoint is the frequency per eye of any corneal infiltrate or any grade 3 or higher SLF including conjunctival injection, corneal edema, corneal neovascularization, corneal staining, tarsal abnormalities, or any other complications. SLFs will be evaluated using the FDA grading scale ranging from 0 to 4, with grade 0 represents the absence of findings and 1 to 4 representing successively worse findings (i.e. Grade 1 = trace, Grade 2 = Mild, Grade 3 = moderate and Grade 4 = severe).

The safety endpoint will be evaluated at 1-, 2-, 4-, 8- and 12-week follow-up visits and during unscheduled visits. Events occurring during an unscheduled visit will be counted in the subsequent scheduled visit. For example, if a SLF grade 3 or higher occurs between Visit 1 and Visit 2, it will be counted in Visit 2. If there are multiple events at a given time point for one eye, it will be counted only once.

The secondary safety endpoint is the frequency per eye of any reported ocular symptoms, problems, or complaints.

The safety endpoints will be evaluated at 1-, 2-, 4-, 8- and 12-week follow-up visits and during unscheduled visits. Events occurring during an unscheduled visit will be counted in the subsequent visit. For example, if an ocular symptom, problem, or complaint is reported between Visit 1 and Visit 2, it will be counted in Visit 2. If there are multiple events at a given time point for one eye, it will be counted only once.

6.2.2. Analysis Methods

Slit Lamp Findings (SLF)

SLF responses will be categorized into a binary outcome as 0 if no Grade 3 or higher SLF or 1 if any Grade 3 or higher SLF. Events occurring during an unscheduled visit will be counted in the subsequent scheduled visit. For example, if a SLF grade 3 or higher occurs between Visit 1 and Visit 2, it will be counted in Visit 2. If there are multiple events at a given time point for one eye, it will be counted only once. The safety endpoint will be analyzed using a Generalized Estimating Equation (GEE) model (Zeger and Liang; 1986)² with a binomial distribution and logit link function. The regression model will include terms for lens group, time (1-, 2-, 4-, 8- and 12-week) and the lens group by time interaction (group*time). Appropriate working correlation matrix will be selected to take on consideration the correlation between measurements within each subject using Quasilikelihood Information Criterion (QIC). Working correlation structures to be considered will include independence (IND), exchangeable (Exch), autoregressive AR(1) and unstructured (UN). The covariance structure that returns the lowest QIC will be selected as the structure that best fit the data. If all model fails to converge, a reduced model will be considered by removing group*time and time from the model.

For unadjusted estimates the odds ratio of outcome 1 between the Test and the Control groups will be calculated with a 95% confidence interval to test for the difference between the Test and Control groups. For adjusted estimates the odds ratio of outcome 1 between the Test and the Control groups will be calculated with a simultaneous 99% confidence interval to test for the difference between the Test and Control groups.

If there are no sufficient SLF findings of Grade 3 or higher, analysis will be performed on any SLF grade 2 or higher SLF. Further analyses by subject, visit and/or slit lamp findings category will also be considered if necessary.

Ocular Symptoms, problems or complaints

Reported ocular symptoms, problems or complaints (0 = No, 1 = Yes) at any visit will be analyzed using a GEE model for clustered binary outcome to assess the difference between the Test and Control groups. The regression model will include terms for lens group, time (1-, 2-, 4-, 8- and 12-week) and the lens group by time interaction. Appropriate working correlation matrix will be selected to take on consideration the correlation between measurements within each subject using Quasi-likelihood Information Criterion (QIC). Working correlation structures to be considered will include exchangeable, autoregressive AR(1) and unstructured (UN).

If the interaction lens by time is significant at the 15% significance level, the difference between the Test and Control will be assessed for each follow-up visit.

For unadjusted estimates the odds ratio of outcome 1 between the Test and the Control groups will be calculated with a 95% confidence interval to test for the difference between the Test and Control groups. For adjusted estimates the odds ratio of outcome 1 between the Test and the Control groups will be calculated with a simultaneous 99% confidence interval to test for the difference between the Test and Control groups.

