1.5. Sample Size Justification

The plan is to enroll 60 eligible subjects per arm with a target completion of 50 subjects per arm. This is a feasibility study and the sample size was not based on any empirical calculation. A statistical power analysis is provided below for different scenarios of size effects.

The power analysis was based on historical data from 3 double masked randomized 2x2 Crossover bilateral multi-site studies [REDACTED] and [REDACTED]. Since this study is a 2-arm parallel study only data from the first period was used from each of the historical studies in the summary below. There is not a historical study available with the same design and lenses, therefore [REDACTED] and [REDACTED] were chosen since both studies contain the Test lens [REDACTED]. The study [REDACTED] was chosen since it contains the Control lens ACUVUE® OASYS®. In all three studies lenses were worn as a daily wear for approximately 2-weeks each. The follow-up visits occurred approximately at 1- and 2-weeks after the

initial visit. Out of 89 subjects enrolled in [REDACTED] 84 (94.4%) completed the study, 4 (4.5%) discontinued and 1 (1.1%) was enrolled but not dispensed (screen failure). Similarly, out of 71 subjects enrolled in [REDACTED] 67 (94.4%) subjects completed the study, and 2 (2.8%) discontinued and 2(2.8%) was enrolled but not dispensed. Lastly, out of 109 subjects enrolled in [REDACTED] 100 (91.7%) completed the study, 6 (5.5%) subjects were discontinued and 3 (2.8%) subjects were enrolled not dispensed. Of all 263 subjects who were dispensed in the studies, 185 (70.3%) were female and 78 (29.7%) were male. The ages of subjects ranged from 18 to 40 years with an average age of 29 years. Table 1 summarizes the primary endpoints data pooled from the three studies for the first period only.

Table 1: Summary of the primary endpoints data pooled from [REDACTED] and [REDACTED] Period 1 Only

SLF Grade 2	Visits			
	1-Week		2-Week	
	Test	Control	Test	Control
Corneal Edema	0(0.0)	0(0.0)	0(0.0)	0(0.0)
Conjunctival Injection	1(0.6)	0(0.0)	1(0.6)	0(0.0)
Tarsal Abnormalities	2(1.2)	11(10.7)	4(2.6)	9(9.0)
Corneal Neovascularization	0(0.0)	18(17.6)	0(0.0)	14(14.0)
Corneal Staining	0(0.0)	1(0.5)	0(0.0)	0(0.0)
Other Findings	0(0.0)	0(0.0)	0(0.0)	0(0.0)
Total Eyes (N)	154	102	150	100
Any SL Grade 2 ^b	3(1.9)	30(29.4)	5(3.3)	23(23.0)
Any SLF Grade 3+	0(0.0)	0(0.0)	0(0.0)	0(0.0)
Total Unique Eyes	154	102	150	100
Total Unique Subjects	77	51	75	50

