% = nx100/N; SD = Standard Deviation

a SLF reported during an unscheduled visit were included in the following scheduled visit.

b The percent (%) of Any SLF Grade 2 is calculated using Total Unique Eyes as a denominator.

Primary Safety Endpoint (Slit Lamp Findings):

The power was estimated from the formula given by Diggle et al. (2002)² for clustered binary data for a pre-specified sample size of N=50 per arm:

$$Z_{\beta} = \frac{\left[\sqrt{\frac{N \cdot \{n(p_1 - p_2)^2\}}{1 + (n-1) \cdot \rho}} - Z_{\alpha} \sqrt{2\bar{p}\bar{q}} \right]}{\sqrt{(p_1 q_1 + p_2 q_2)}}$$

where p_1 : Response proportion in group 1 (Test), $q_1 = 1 - p_1$, p_2 : Response proportion in group 2 (Control), $q_2 = 1 - p_2$, $\bar{p} = (p_1 + p_2)/2$, $\bar{q} = 1 - \bar{p}$, n : number of observations per cluster(n was set to 10; 2 eyes x 5 time points), N is the number of subjects per arm and ρ is the common correlation across the n observations. The term z_{α} is the z score that correspond to the pre-specified type I error error α . The term z_{β} is the z score that corresponds to the estimated power $1 - \beta$ for pre-specified size effects.

There were no SLF of grade 3 or 4 reported in any of the three studies. Using previous research in the *literature*^{4,5}, the anticipated proportion of eyes with any SLF grade 3 and 4 is estimated to be less than or equal to 0.5% in both test and control arms.

Table 2: Power calculation for various effect sizes and correlations for SLF

Test Proportion	Control Proportion	Delta	Rho	Power
0.001	0.0510	.005	0.25	33%
0.001	0.0510	.005	0.50	58%
0.001	0.0510	.005	0.75	71%
0.0025	0.0525	.005	0.25	36%
0.0025	0.0525	.005	0.50	61%
0.0025	0.0525	.005	0.75	73%
0.005	0.0550	.005	0.25	40%
0.005	0.0550	.005	0.50	64%
0.005	0.0550	.005	0.75	75%
0.01	0.0600	.005	0.25	48%
0.01	0.0600	.005	0.50	69%
0.01	0.0600	.005	0.75	78%

Primary Efficacy Endpoint (Visual Acuity):

The power calculations were performed using Diggle's formula (*Diggle et al.*; 2002)² for clustered continuous data for a pre-specified sample size of N=50 per arm:

$$Z_{\beta} = \sqrt{0.5 * \left(\frac{N(n[\frac{\mu_1 - \mu_2}{\sigma^2}]^2)}{1 + (n-1)\rho} \right)} - Z_{\alpha}$$

Where σ^2 is the assumed common variance in the two groups, $\mu_1 - \mu_2$: the difference in means between the two groups (Test - Control), n : number of observations per cluster, N is the number of subjects per arm and ρ is the common correlation across the n observations.

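### At the SAP's expected event rate the primary slit lamp GEE is almost never estimable, its reduced model cannot handle an empty arm, and the last fallback changes the endpoint on a trigger with no number

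*SAP*

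**What the plan says.** SAP 6.2.2 (repeated in Protocol 9.1) codes each eye at each visit as having or not having a grade 3 or higher finding. It fits a logit GEE with lens group, five visits and their interaction, and takes a Test-versus-Control odds ratio with 95% and 99% intervals. Two fallbacks follow. The first is "If all model fails to converge, a reduced model will be considered", obtained by dropping the interaction and time. The second is "If there are no sufficient SLF findings of Grade 3 or higher, analysis will be performed on any SLF grade 2 or higher SLF". The SAP gives no event count for sufficiency, no order between the two steps, and no method for an arm with no events.

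On how many events to expect, SAP 1.5 says "the anticipated proportion of eyes with any SLF grade 3 and 4 is estimated to be less than or equal to 0.5" percent in both arms, and that "There were no SLF of grade 3 or 4 reported in any of the three studies". It does not say whether the rate is per visit or over the study.

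The primary safety hypothesis (SAP 1.4.1, Protocol 4.1.3) is on grade 3 or higher. SAP 6.2.1 defines the endpoint more widely, as a corneal infiltrate or a grade 3 or higher finding; the binary outcome in 6.2.2 leaves infiltrates out.

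**The concern.** The full model is saturated: ten parameters (intercept, 1 for group, 4 for time, 4 for interaction) for ten arm-by-visit cells. Any cell without an event has a log odds of minus infinity, so at least one visit's comparison has no finite value. Dropping the time terms leaves a single odds ratio, which is zero or infinite if one arm has no events and undefined if both have none.

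The second fallback then changes the question. A named primary hypothesis on grade 3 findings would be replaced by a comparison of milder findings, on a judgement of sufficiency that the SAP does not quantify. SAP Table 1 shows why the choice of grade could matter: any grade 2 finding was 1.9% on Test and 29.4% on Control at week 1, and 3.3% and 23.0% at week 2, with no grade 3 findings in either. Those figures come from different studies and say nothing reliable about this comparison, but they show that the grade chosen could decide the conclusion.

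**Working it through.** **Inputs.** Rate p = 0.005, the ceiling in SAP 1.5. Arm size 50 ("for a pre-specified sample size of N=50 per arm") and 60 ("The plan is to enroll 60 eligible subjects per arm with a target completion of 50 subjects per arm"); the safety set is all dispensed subjects, so up to about 60. Ten observations per subject ("n was set to 10; 2 eyes x 5 time points"). Correlation 0.25 to 0.75, as in SAP Table 2, with 0 and 1 as limits.

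**The plan's own figure.** Table 2 does not reproduce as power. For 0.005 against 0.055 at correlation 0.25, the printed formula at two-sided 0.05 gives z = [√(50·10·0.05²/3.25) − 1.96·√(2·0.03·0.97)]/√0.05695 = (0.620 − 0.473)/0.239 = 0.62, or 73% power against the stated 40%. All 12 rows equal one minus power at one-sided 0.01, and the printed difference of .005 should be .05. That is a separate matter; nothing below depends on it.

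**Full model, 0.5% read per eye-visit.**

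- 50 per arm, independence: P(cell empty) = 0.995^100 = 0.606; P(all ten filled) = (1 − 0.606)^10 = 0.009%.
- 60 per arm, independence: 0.995^120 = 0.548; (1 − 0.548)^10 = 0.04%.
- 50 per arm, simulated exchangeable data (40,000 trials per setting): 0.7%, 2.4% and 4.5% at correlation 0.25, 0.50 and 0.75.
- Full correlation: (1 − 0.995^50)² = 4.9% with 50 per arm; (1 − 0.995^60)² = 6.7% with 60.

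These use one common correlation across eyes and visits, as SAP 1.5 does. If findings persisted through every visit but eyes were independent, the figure with 60 per arm would be (1 − 0.548)² = 20%. Such persistence is hard to square with the Protocol 4.7.1 note at each follow-up that subjects must be free of grade 3 findings. Rates below the 0.5% ceiling lower every figure.

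**Reduced model: P(at least one arm empty) = 1 − (1 − q)², where q = P(a given arm is empty).**

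| Reading of 0.5% | Per arm | q | At least one arm empty |
|---|---|---|---|
| Per eye over study, independent eyes | 60 | 0.995^120 = 0.548 | 80% |
| Per eye over study, concordant eyes | 60 | 0.995^60 = 0.740 | 93% |
| Per eye-visit, independent | 60 | 0.995^600 = 0.049 | 10% |
| Per eye-visit, independent | 50 | 0.995^500 = 0.082 | 16% |
| Per eye-visit, correlation 0.75, simulated | 60 | – | 75% |
| Per eye-visit, correlation 0.75, simulated | 50 | – | 80% |

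The last two rows depend on how the correlation arises. If a subject's ten observations are identical with probability 0.75 and otherwise independent, P(subject free of events) = 0.75·0.995 + 0.25·0.995^10 = 0.9840. Then q = 0.9840^60 = 0.381 and at least one arm is empty in 62% of trials (69% with 50 per arm). A beta-binomial, which concentrates events in fewer subjects, gives P(subject free) = 0.9910 and 82% (87% with 50 per arm). Roughly 60% to 80%, or slightly above, is a fair summary.

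**Does the convergence trigger fire?** Test fits in one package (Python statsmodels) suggest it may not. With 2 events against 0, the group-only GEE reported convergence, with a log odds ratio of −23.0 and a standard error of 0.71: a spuriously significant result. The full model with 2 against 3 events also reported convergence, with a standard error that was missing or in the thousands. The group-only model with 2 against 3 events was sound (log odds ratio 0.41, standard error 0.89).

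**The case against.** The plan has fallbacks, and on one reading the first often works. If 0.5% is per eye-visit and observations are close to independent, both arms have events in 84% to 90% of trials and the group-only odds ratio exists. A reader might infer that the planned primary safety analysis is almost certain to fail altogether. The documents do not support that: it holds for the full interaction model, while for the group-only model it depends on a time base and a correlation that the SAP leaves open. Infiltrates, if counted as SAP 6.2.1 says, would also add events.

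A reader might also infer that a grade 3 signal against Test would be hidden, or that the switch would be made with lens assignments known. Neither is supported. Protocol 9.1 asks for descriptive statistics by lens for all safety variables, Protocol 8.1 for listings of all safety data, and Protocol 8.3 counts other grade 3 corneal findings as significant adverse events. Grade 2 or higher includes every grade 3 event. SAP 6.2.2 allows further analyses by subject, visit or category. No document says who applies the sufficiency judgement or when.

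The hypotheses are declared exploratory (Protocol 3.1, SAP 1.4), which lowers the consequence. What remains is that no provision gives a formal grade 3 comparison when an arm is empty, and none puts a number on the trigger. SAS may report convergence differently from the package used here, but the SAP contains no check for separation.

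**Conclusion.** The concern stands in a bounded form. Under the SAP's common-correlation assumption and a per-visit rate of 0.5%, the full GEE has an event in every cell in about 0.01% of trials (independence, 50 per arm) to about 7% (full correlation, 60 per arm). The reduced model's failure is conditional on an empty arm, and its frequency runs from about 10% to 93% according to the reading of the rate and the correlation. All of this counts grade 3 findings only, at the 0.5% ceiling. What can be lost is the formal grade 3 comparison, not sight of the events. This should be corrected, but in an exploratory study it does not block the trial.

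**What to change.** Make the primary safety comparison one that works with sparse or empty arms, and always report it. Use the endpoint as SAP 6.2.1 defines it (infiltrate or grade 3 or higher), per subject, in either eye at any visit through week 12. Give the Test-minus-Control risk difference with an exact unconditional 95% interval and test. Exact methods give usable answers where the odds ratio does not: 6/60 against 0/60 has a two-sided Fisher p of 0.027, and 0/60 has an exact 95% upper limit for that arm's risk of 1 − 0.025^(1/60) = 6.0%.

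Keep the GEE as supplementary, fitted only if a minimum event count per arm, written into the SAP before unmasking, is reached. At 0.5% of eyes over the study only 120 × 0.005 = 0.6 affected eyes are expected per arm, so it would seldom be run. Report grade 2 or higher as a separate supportive analysis, never as a replacement. State the time base of the 0.5%.

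The cost is SAP wording and a short exact program, plus protocol wording: the SAP supersedes only section 9 of the protocol, so the per-eye, by-visit hypotheses in SAP 1.4.1 and Protocol 4.1.3 must both be aligned. The by-visit, per-eye odds ratio becomes supplementary.

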4.4.2 OPTIONAL FLOWCHART

4.5 RANDOMIZATION AND MASKING

Subjects will be randomly assigned to either JJVCI Investigational Contact Lens (Test) or ACUVUE OASYS (Control) groups based on a computer-generated randomization schedule prepared before the study by the sponsor Biostatistician. The randomization will be stratified by study site and randomly permuted blocks of 4 assignments will be used to achieve 1:1 Test versus Control lens type ratio within each study site.

The study site must follow the randomization scheme provided and complete enrollment according to the randomization list and not pre-select or assign subjects. The randomized assignment of subjects will be performed at the first visit prior to the first fitting. The following must have occurred prior to randomization:

- Informed consent has been obtained
- Subject meets all the inclusion / exclusion criteria
- Subject history and baseline information has been collected

This is a partially subject masked study. The dynamic nature (variable shade) of the Test lens makes full masking impossible. However, the identity of the Control lenses will be masked to the subject by way of investigational foil. This will reduce the likelihood that habitual wearers of ACUVUE OASYS recognize the Control lens and increase the likelihood that questionnaires will be answered unbiasedly.

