1.6. Randomization and Masking

Subjects will be randomly assigned to either J JVCI Investigational Contact Lens (Test) or ACUVUE® OASYS® (Control) groups based on a computer-generated randomization schedule prepared before the study by the study biostatistician. The randomization will be stratified by study site and randomly permuted blocks of 2 assignments will be used to achieve 1:1 test versus control lens type ratio within each study site. The assignment of subjects will be performed at the first visit prior to the first fitting. The following must have occurred prior to assignment:

- Informed consent has been obtained
- It has been determined that the subject meets all the inclusion / exclusion criteria
- Subject history and baseline information has been collected

When the trial fitting assessment is ready to be conducted, the following steps should be followed:

1. Investigator or designee (documented on the Delegation Log) will consult the randomization scheme to obtain the study test article assignment for that subject prior to dispensing.
2. Investigator or designee will record the subject's number on the appropriate line of the randomization scheme.

3. Investigator or designee will pull the appropriate test articles from the study supply. All test articles that were opened, whether dispensed or not, must be recorded on the Test Article Accountability Log in the “Lenses Dispensed” section.

This will be a partially-masked study. The identity of the study lenses will be masked to the subject and as much as possible to the investigator.

The following procedures will be followed:

- Subjects will not be aware of the identity of the study contact lenses.
- Investigators involved in the data collection will be masked as to the identity of the study lenses.

This is a partially-masked study. The dynamic nature (variable shade) of the Test lens makes full masking impossible. However, the identity of the Control lenses will be masked to the subject by way of investigational foil. This will reduce the likelihood that habitual wearers of ACUVUE OASYS recognize the Control lens and increase the likelihood that questionnaires will be answered unbiasedly.

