5.2.2. Analysis Methods

Efficacy Analysis:

Visual Acuity

Contact lens monocular distance best-corrected visual acuity (BCVA) on LogMAR scale will be analyzed using a linear mixed model to test for the differences between the Test and Control group at each follow-up visit. Lens group, time (1-, 2-, 4-, 8- and 12-weeks) and the interaction between lens and time will be included as fixed effects in the model; and investigator site, subject and eye nested within subject as random effects when appropriate. The covariance between residuals from the same eye and subject at different time points will be selected based on the finite-sample Corrected Akaike's Information Criterion. Covariance structures considered include Compound Symmetry (CS), Heterogeneous Compound Symmetry (CSH), Spatial Power (SP(POW)), *Ante*-dependence (ANTE(1)) and unstructured (UN). For ANTE (1) and SP (POW) structures, site, subject and eye nested within subject will be included as random effects. For the remaining structures only site and subjects will be included as random effects. The covariance structure that returns the lowest Akaike Information Criteria Corrected (AICC) will be selected as the structure that best fit the data. Heterogeneous residuals covariance structures (R-side) across lens groups will be considered when appropriate. The log-likelihood ratio test will be used to test for the homogeneity between the residual covariance structures. The Kenward and Roger method will be used for the denominator degree of freedom.

Comparisons between the Test and the Control groups will be conducted at each time point using a t-test on least-square means from the repeated measure analysis. Adjustment for multiple comparisons across time will be performed using Bonferroni's method with alpha equal to 0.01(0.05/5). The corresponding simultaneous confidence intervals of least-square means differences will be calculated with 99% confidence. Unadjusted multiple comparisons will be calculated with 95% confidence for each comparison.

Average Wear Time (AWT)

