Eyestrain items will be scored using item response theory. A lower score indicates less eyestrain, whereas higher score indicates more eyestrain. Eyestrain score will be analyzed using a linear mixed model to test for difference between the Test and the Control groups. Lens Group, time (2-, 4-, 8- and 12-week), iris category and all interactions between lens group, time and iris category will be included as fixed effects in the model; and site as random effect. The covariance between residuals from the same subject at different time points will be selected based on the finite-sample corrected Akaike's Information Criterion. Covariance structures considered include homogenous compound symmetry (CS), heterogeneous Compound symmetry (CSH), Spatial Power (SP (POW)), Ante-dependence (ANTE (1)) and unstructured (UN). For ANTE (1) and SP (POW) structures, site and subject will be included as random effects. For the remaining structures only site will be included as random effect. The covariance structure that returns the lowest AICC will be selected as the structure that best fit the data. Heterogeneous residuals covariance structures (R-side) across lens groups will be considered when appropriate. The log-likelihood ratio test will be used to test for the homogeneity between the residual covariance structures. The Kenward and Roger method will be used for the denominator degree of freedom.

If the interaction between lens and iris category is significant at the 15% significance level, then comparison between lenses within each iris category will be conducted. If the interaction between lens, iris category and time is significant at the 15% significance level, then comparison between lenses within each iris category at each timepoint will be conducted.

Comparison between the Test and the Control groups will be conducted at each time point using a t-test on least-square means from the repeated measure analysis. Adjustment for multiple comparisons across time will be performed using Bonferroni's method with alpha equal to 0.0125 (0.05/4). The corresponding simultaneous confidence intervals of least-square means differences will be calculated with 98.75% confidence. Unadjusted multiple comparisons will be calculated with 95% confidence for each comparison.

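### The ocular symptom and slit lamp GEEs omit site although randomization is stratified by it; if rates differ between sites, these safety comparisons are conservative, by an amount the documents do not fix

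*SAP*

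**What the plan says.** Allocation: SAP 1.6 states that "The randomization will be stratified by study site", and Protocol 4.5 says the same. The block sizes differ (4 in the protocol, 2 in the SAP), but either one balances the arms within site, so this point does not depend on which is used.

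Continuous endpoints (SAP 5.2.2): the visual acuity model has "investigator site, subject and eye nested within subject as random effects when appropriate". The wear time and eyestrain models have fixed effects "and site as random effect".

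Binary endpoints (SAP 6.2.2): for ocular symptoms, "The regression model will include terms for lens group, time (1-, 2-, 4-, 8- and 12-week) and the lens group by time interaction". The slit lamp model lists the same three terms. In both, the working correlation is chosen by QIC for measurements within a subject. Site therefore enters neither the mean model nor the correlation. Protocol 9.1 specifies the same two models. SAP 2.1 justifies pooling centers on procedural grounds and adds no site term.

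If grade 3+ slit lamp findings are too few, SAP 6.2.2 moves the analysis to grade 2 or higher.

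**The concern.** Stratified allocation removes between-site differences from the true sampling variability of the lens contrast. An analysis that ignores site still counts those differences as error. Its standard error is then larger than the actual spread of the estimate, and the test rejects less often than its nominal level.

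That would normally be the cautious side on which to err. Here it is not. The slit lamp and symptom hypotheses (SAP 1.4) are that Test is statistically no different from Control, so non-significance is the hoped-for result. A conservative test makes a real excess of symptoms or findings easier to miss. The SAP gives no reason for treating the binary endpoints differently from the continuous ones.

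**Working it through.** **The plan's own figure.** No power is given for ocular symptoms. The only stated power for a binary GEE is SAP Table 2 (slit lamp). Its first row has p = 0.001 vs 0.051, N = 50, n = 10, rho = 0.25.
- Square-root term: √(50 × 10 × 0.05² / 3.25) = 0.620.
- √(2p̄q̄) = √(2 × 0.026 × 0.974) = 0.225, and √(p₁q₁ + p₂q₂) = 0.222.
- At two-sided 5%: z = (0.620 − 1.96 × 0.225)/0.222 = 0.81, so power is 79.0%. The table prints 33%.
- With 2.326 in place of 1.96, power is 66.8%, and 1 − 0.668 = 33.2%. All twelve rows match the type II error computed this way.

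That is a separate matter. Table 2 contains no site component, and nothing below depends on it.

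**Mechanism.** On a linear scale, with n subjects per arm balanced within site, the true variance of the arm difference is 2σ_w²/n. An analysis without site estimates 2(σ_w² + σ_s²)/n. The two agree only if the between-site variance σ_s² is zero.

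**Inputs from the documents.** 6 sites with 15-25 subjects each, taken as 20 (Protocol 4.4); 1:1 permuted blocks of 4 within site (Protocol 4.5); 2 eyes × 5 visits = 10 observations per subject (SAP 1.5); two-sided 5% (SAP 6.1.1).

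**Assumptions not in the documents.** Baseline symptom rate 10% or 25%; between-subject SD 1.0 or 1.5 and between-site SD 0 to 1.0, on the logit scale; conditional log odds ratio 0.7 (odds ratio about 2).

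**Method.** Logistic GEE for the lens main effect with subject-clustered robust SE, fitted without and with site as a fixed factor to the same simulated trials, 2,000 per scenario. The Monte Carlo SE is at most √(0.25/2000) = 1.1 points for power and about 0.5 points for size. Site ICC = σ_s²/(σ_s² + σ_subject² + 3.29). At most 1% of trials in any scenario could not be fitted.

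| Site SD | Site ICC | SE ÷ true SD, no site | Type I error, no site | Example power, no site → site* | Power gain, all scenarios |
|---|---|---|---|---|---|
| 0 | 0 | 0.98-1.01 | 4.9-5.4% | 86.2 → 86.4% | none |
| 0.3 | about 0.02 | 0.99-1.03 | 4.4-5.3% | 84.9 → 85.7% | about 1 point |
| 0.5 | 0.04-0.06 | 1.04-1.09 | 3.5-4.4% | 81.8 → 85.5% | about 3-4 |
| 0.8 | 0.10-0.13 | 1.05-1.14 | 2.6-4.2% | 74.7 → 83.4% | about 5-9 |
| 1.0 | 0.15-0.19 | 1.08-1.19 | 2.2-4.1% | 68.5 → 83.1% | about 9-15 |

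*Baseline 25%, subject SD 1.0.

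With site in the model, SE ÷ true SD is 0.98-1.03 and type I error 4.2-5.8% throughout.

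**Where the gap comes from** (example row, site SD 1.0). The mean odds ratio is 1.70 without site and 1.82 with it; the mean SEs are 0.220 and 0.204.
- Wald ratio without site: ln 1.70/0.220 = 0.531/0.220 = 2.41.
- Wald ratio with site: ln 1.82/0.204 = 0.599/0.204 = 2.94.
- The ratio 2.94/2.41 = 1.22 splits into 0.599/0.531 = 1.13 (odds ratio further from 1) and 0.220/0.204 = 1.08 (smaller SE).
- Against the actual spread of the estimates (0.183 and 0.204), the signals are 0.531/0.183 = 2.90 and 0.599/0.204 = 2.94.

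The estimate without site therefore carries nearly the same information. What is wrong is its standard error relative to its own variability.

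**Grade 3+.** SAP 1.5 expects at most 0.5% of eyes. Taken per observation, that is 20 × 10 × 0.005 = 1 event per site. Under independence a given site has no event with probability 0.995²⁰⁰ = 0.37, and at least one of six has none with probability 1 − (1 − 0.367)⁶ = 0.94. With assumed subject and site SDs of 0.5, the simulated figure was 91%. Fixed site effects are not estimable there.

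**The case against.** **The size is unknown, and the large figures need large site differences.** This stands. With baseline log-odds −1, a site SD of 1.0 puts 95% of sites between about 5% and 72% for a typical subject; 0.5 gives 12% to 50%. Nothing in the documents points to 1.0. Symptoms are reported by the subject on a questionnaire, so grading differences between site staff are not a natural source of variation for that endpoint.

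**Table 1 as evidence of site or grader differences.** A reader might infer such differences from the historical grade 2 rates (1.9% and 3.3% on Test, 29.4% and 23.0% on Control). The documents do not support that. Two of the three studies contained the Test lens and a third the Control, so lens and study are confounded, and no site-level data are shown. This trial also excludes grade 2+ findings at baseline.

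**The power comparison is not size-matched.** This also stands. In a separate run of 4,000 trials (6 × 20 subjects, 5 observations each, subject SD 1), power at site SD 1.0 was 60% without site and 74% with it at the nominal level, but 69% and 71% once both tests were calibrated to 5%. At SD 0.5 the calibrated figures were 75% and 76%. The loss is therefore almost all conservatism. It is still real, because the SAP will use nominal levels. Type I error with site in that run was 5.3-6.1%, so the adjusted test may be slightly liberal.

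**The weightier flaw is reading non-significance as no difference.** Agreed. Site adjustment does not cure that.

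**Conclusion.** The omission is plain in both GEEs, and so is the direction: if rates differ between sites, the lens comparison is conservative. A reader might go further and conclude that the planned standard errors are too large as a matter of fact. The documents do not support that, because they give no between-site variance, no ICC and no expected symptom rate.

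The size is conditional on the assumed site SD: nothing noticeable up to 0.3, about 3-4 points of power at 0.5 and about 9-15 at 1.0, for an odds ratio of about 2 tested at 5%. Part of that gap reflects the marginal odds ratio lying closer to 1 than the site-conditional one. The 99% adjusted intervals and the individual visit contrasts were not simulated.

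The practical weight falls on ocular symptoms and on the grade 2+ fallback, not on grade 3+. Severity is minor: SAP 1.4 calls all hypotheses exploratory, and symptoms are a secondary endpoint.

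**What to change.** - **Ocular symptoms:** add site as a fixed factor to the GEE.
- **Grade 2+ slit lamp findings:** add site when every site has events. State in advance what happens otherwise: merge small or zero-event sites, or drop site. The rule is needed. At 2-3% per eye-visit, at least one of six sites had no event in 7% to 73% of simulated trials (assumed subject SD 1.5-2.5, site SD 0-1).
- **Grade 3+ slit lamp findings:** leave site out.

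The cost is one model term, or five parameters with six sites. The odds ratio becomes conditional on site and should be labelled so. Because type I error with the robust SE may run slightly above 5%, a small-sample correction to that SE is advisable.
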